12.4 Confidence intervals

Regardless of results in hypothesis testing, the calculated ratios and differences in between-group comparisons will be complemented with confidence intervals (usually at 95% level but 90% for non-inferiority studies), for descriptive purpose. For the quantitative outcomes, confidence intervals will be based on t-test. For binary outcomes, the confidence intervals will be based on binomial distribution.

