1.3 Exploratory analyses

Exploratory analyses will be described later, in separate SAP or in addenda to this SAP. Note that in the sister trial in Burkina Faso ("iLiNS-ZINC"), there is a pre-planned exploratory analysis: description of child feeding practices and factors associated with these practices including food security and seasonality, and relation with nutritional status (growth, iron status, morbidity).

3. Hypotheses to be tested

Stated qualitatively: Provision of LNS would not impact infant and young child feeding practices. More specifically, provision of LNS would not cause a change in:

- Breastfeeding (prevalence of any breastfeeding several time points throughout intervention, and reported frequency of breastfeeding the previous day)
- Frequency of feeding other solids foods (meals and snacks, or feeding episodes)²;

²These data are not yet available and variable construction and analyses are not described in this version.

- Dietary diversity measured as food group diversity at or above the WHO cut-off³;
- Number of nutrient-dense food groups (animal-source foods, fruits and vegetables)

4. Description of infant and young child feeding practice outcome variables

On the following pages, we present information on construction of outcome variables.

The table shows details on: data sources; variable names and variable construction; treatment of data and criteria for imputing missing values.

With few exceptions (detailed in the table) no data will be imputed for analyses of IYCF practices as outcomes.

However, in later analyses where longitudinal IYCF practice variables (e.g. indices summed across time points) may be used as potential effect modifiers, data could be imputed to avoid losing substantial numbers (those for whom data from all time points are not available).

Timing of outcomes: in the iLiNS-DOSE trial, target dates for collection of IYCF practices data were: Baseline (week 0, at ~5.5-6.5 mo of age); week 16; week 28; week 40; and endline (week 52). Data on breastfeeding practices, food group intake, and use of fortified products and vitamin/mineral drops were assessed at all time points. Data on frequency of meals and snacks were collected on KAP questionnaires at 6, 12, and 18 months of age (data not yet available).

³ WHO (2008) Indicators for assessing infant and young child feeding practices: conclusions of a consensus meeting held 6–8 November 2007 in Washington D.C., USA.

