\sim 12 mo: ASF score (out of 28)		As for ~9.6 m	onth time point		
~12 mo: Lowest ASF tertile (%)	As above	Constructed as above. New variables are asf7T28, and i28_asfT1 through i28_asfT3.	As above		
~12 mo: Fruit/veg score (out of 35)		As for ~9.6 m	onth time point		
~12 mo: Lowest fruit/veg tertile (%)	As above	Constructed as above. New variables are frveg7T28, and i28_frvegT1 through i28_frvegT3.	As above		

Page 14	of 27
---------	--------------

Outcome	Variable name(s)	Location, variable construction	Criteria for errors, outliers	Criteria for transformation	Use of imputation			
~15 mo: Lowest ASF tertile (%)	As above	Constructed as above. New variables are asf7T40, and i40_asfT1 through i40_asfT3.	As above					
~15 mo: Fruit/veg score (out of 35)		As for ~9.6 m	onth time point					
~15 mo: Lowest fruit/veg tertile (%)	As above	Constructed as above. New variables are frveg7T40, and i40_frvegT1 through i40_frvegT3.	As above					
~18 mo: ASF score (out of 28)		As for ~9.6 m	onth time point					
~18 mo: Lowest ASF tertile (%)	As above	Constructed as above. New variables are asf7T52, and i52_asfT1 through i52_asfT3.	As above					
~18 mo: Fruit/veg score (out of 35)	As for ~9.6 month time point							
~18 mo: Lowest fruit/veg tertile (%)	As above	Constructed as above. New variables are frveg7T52, and i52_frvegT1 through i52_frvegT3.	As above					

5. Approach to analysis and exclusions specific to this analysis

All tests will be two-sided, at 5% level of significance.

Since varying numbers of observations are available depending on the time point (i.e., there were a substantial number of missed visits), sample sizes by group will be reported for each time point. If specific outcome variables are missing for more than 10% of infants (with denominator being total records available for the time point) we will report the number of observations used per specific outcome analysis.

First analysis will be by intention-to-treat, but excluding observations that are more than ± 4 weeks (28 days) from the median observed age for visits 0, 16, 28 and 40. That is, at time points, 0, 16, 28 and 40, child age could vary by up to 8 weeks.

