5.4 Analysis of the effect of the intervention

General comments:

- a. The hypothesis stated in section 3 is a non-equivalence hypothesis. However, the study was not powered for IYCF practices outcomes and we are severely underpowered for equivalence analyses, particularly for dichotomous outcomes (such as prevalence of continued breastfeeding at any time point). Therefore the more traditional approach in the nutrition literature of analyzing for significant differences will be followed in the first instance. This limitation will be clearly explained in the discussion section of any publication.
- b. For quasi-continuous variables, we will supplement this with an equivalence approach to hypothesis testing, to help inform conclusions from this analysis.

Analysis of the effect of the intervention will follow these steps:

- a. A set of pre-specified potential covariates will be examined through reviewing correlations and collinearity (e.g. using "collin" command in Stata). Variables with VIF > 10 will be assessed and a reduced set of variables will be retained, such that all VIF are < 10.
- b. We will test the null hypothesis of no difference among the four treatment groups (iLiNS-DOSE) using ANCOVA or logistic regression, and controlling for the prespecified covariates (most of which are also potential effect modifiers, see below).
- c. For all analyses, if the global null hypothesis is rejected at 0.05 level, then we will perform post-hoc pairwise comparisons of all four groups using appropriate

adjustments for multiple comparisons and Scheffe's test to examine other contrasts of interest.

- d. The effects of potential effect modifiers will be assessed with an interaction term in the ANCOVA or logistic regression model. Each interaction will be assessed separately.
- e. Significant interactions (p < 0.05) will be further examined with stratified analyses, estimation of separate regression lines, or estimation of adjusted means at key points of the covariate, in order to understand the nature of the effect modification.

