5.7 Future exploratory (path) analyses

There are a number of potential effect modifiers not yet available, but which could interact with provision of LNS to produce differential effects. These may be included in later exploratory analyses:

- Household
 - Proxy for income (expenditures)
 - o Grandmother lives on compound/with the child
- Maternal
 - o Index for responsive feeding (composite from KAP)
 - o Maternal decision-making power (composite from KAP)
 - o Maternal depression
- Child
 - o Morbidity

o Appetite

7. Design of tables and figures

See following pages for a list of tables and example figures that will be examined by the manuscript writing group:

Table 1.	Number of observations and missing visits, by intervention group and by time point					
Table 2.	Background characteristics of study participants, baseline and endline samples, by intervention group					
Table 3.	Feeding practices at enrollment, by intervention group					
Table 4a.	Continued breastfeeding and frequency of breastfeeding yesterday, by intervention group					
(Table 4b.	Continued breastfeeding and frequency of breastfeeding yesterday, pairwise comparisons. This table, with pairwise comparisons, will be prepared if overall tests are significant)					
Table 5a	Infant diet quality yesterday: food group diversity & nutrient-dense food groups by intervention group					
(Table 5b	Infant diet quality yesterday: food group diversity & nutrient-dense food groups, pairwise comparisons. This table, with pairwise comparisons, will be prepared if overall tests are significant)					
Table 6a	Infant diet quality last week: nutrient-dense food groups, by intervention group					
(Table 6b	Infant diet quality last week : nutrient-dense food groups, pairwise comparisons This table, with pairwise comparisons, will be prepared if overall tests are significant)					
Example figures (final set of figures to be determined):						

Figure 1	Participant flow
Figure 2	Breastfeeding practices, by intervention group
Figure 3	Nutrient-dense food groups yesterday, by intervention group
Figure 4	Possibly, a Figure illustrating comparison between adjusted confidence intervals and equivalence margins

Table 1. Number of observations and missing visits, by time point (FFQ)

Age ^a	X.X mo			X.X mo			XX.X mo				XX.X mo				XX.X mo					
Group ^b	0	10	20	40	0	10	20	40	0	10	20	40	0	10	20	40	0	10	20	40
Number permanently																				
lost to follow-up																				
Number missing																				

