Number of infants at enrollment. For exclusive breastfeeding n is the number of infants who were less than 6 months of age at enrollment.

^b LNS=lipid-based nutrient supplement; the quantities indicated are the size of the infant's daily dose, delivered to the household [indicate weekly or bi-weekly].

^c Comparison between intervention groups; p-value for ANOVA (continuous and quasi-continuous variables) or chi-square test (categorical variables).

^d Exclusive breastfeeding defined based on negative responses to a series of questions on fluids, semi-solids and solids consumed yesterday.

^e Respondents were asked if the baby was breastfed yesterday and if so they were read the following options: Only at night; only 1 or 2 times during the day; about 3 to 5 times during the day; at least 6 times during the day.

^f Respondents were asked (yes/no) if the infant was given any of a list of fluids and semi-solids yesterday, and solid food consumption was determined using an open, guided recall of the previous day (qualitative 24-hour recall). Foods reported in the recall were circled and coded into groups.

	N^{a}	(missing)	Control	LNS ^b 10 g	LNS 20 g	LNS 40 g	All	P-value ^c
Frequency of breastfeeding ^d								
At ~ X.X mo ^e (%)								
None								
6+ times								
At ~ XX.X mo (%)								
None								
6+ times								
At ~ XX.X mo (%)								
None								
6+ times								
At ~ XX.X mo (%)								
None								
6+ times								

Table 4a. Frequency of breastfeeding yesterday, by intervention group

^a Number of infants not permanently lost to follow-up at each age/time point.

^b LNS=lipid-based nutrient supplement; the quantities indicated are the size of the infant's daily dose, delivered to the household [indicate weekly or bi-weekly].

^c Values presented are unadjusted prevalences. Statistical tests are for adjusted analyses: logistic regression, controlling for.....

^d Respondents were asked if the baby was breastfed yesterday and if so they were read the following options: Only at night; only 1 or 2 times during the day; about 3 to 5 times during the day; at least 6 times during the day.

^e Approximate age shown is median observed age. After enrollment, additional data collection time points for infant feeding practices were: 16 weeks, 28 weeks, 40 weeks, and 52 weeks of participation in the study.

Table 5a Infant diet quality yesterday: food group diversity & nutrient-dense food groups

	N ^a	(missing)	Control	LNS ^b	LNS	LNS	Δ11	P-

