	19	(missing)	Control	10 g	20 g	40 g	All	value ^c
Food groups consumed by the infant yesterday ^{d}								
At ~ X.X mo ^e (%)								
4+ food groups (WHO indicator ^f , %)								
No ASF ^g (%)								
Mean or median $\#$ ASF groups (of 5) ^h								
No fruits/vegetables (%)								
Mean or median # fruit/vegetable groups $(of 5)^{i}$								
At ~ XX.X mo (%)								
4+ food groups (WHO indicator, %)								
No ASF(%)								
Mean or median # ASF groups (of 5)								
No fruits/vegetables (%)								
Mean or median # fruit/vegetable groups (of 5)								
At ~ XX.X mo (%)								
4+ food groups (WHO indicator, %)								
No ASF(%)								
Mean or median # ASF groups (of 5)								
No fruits/vegetables (%)								
Mean or median # fruit/vegetable groups (of 5)								
At ~ XX.X mo (%)								
4+ food groups (WHO indicator, %)								
No ASF(%)								
Mean or median # ASF groups (of 5)								
No fruits/vegetables (%)								
Mean or median # fruit/vegetable groups (of 5)								

^a Number of infants not permanently lost to follow-up at each age/time point.

^b LNS=lipid-based nutrient supplement; the quantities indicated are the size of the infant's daily dose, delivered to the household [indicate weekly or bi-weekly].

^c Values presented are unadjusted means (SD) or medians (I-Q ranges) and prevalences. Decision on presenting means or medians will be made after examination of distributions. Statistical tests are for adjusted analyses; analysis of covariance and logistic regression, controlling for...

^d Respondents were asked (yes/no) if the infant was given any of a list of fluids and semi-solids yesterday, and solid food consumption was determined using an open, guided recall of the previous day (qualitative 24-hour recall). Foods reported in the recall were circled and coded into groups.

^e Approximate age shown is median observed age. After enrollment, additional data collection time points for infant feeding practices were: 16 weeks, 28 weeks, 40 weeks, and 52 weeks of participation in the study.

^f The WHO indicator sums seven food groups and a score of 4 or more of 7 is associated with higher nutrient density (WHO, 200X); the food groups are: 1) grains, roots and tubers; 2) legumes and nuts; 3) dairy products; 4) flesh foods; 5) eggs; 6) vitamin-A rich fruits and vegetables; and 7) other fruits and vegetables.

^g ASF=animal-source food.

^h The 5 ASF groups are: 1) organ meats; 2) other meat/poultry; 3) fish; 4) eggs; and 5) dairy.

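### Appendix 05: after a non-significant global test, the yes/no feeding outcomes are tabulated with no LNS-control estimate or interval, although the hypothesis is one of no impact

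*SAP*

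**What the plan says.** Section 3 of Appendix 05 states the hypothesis as "Provision of LNS would not impact infant and young child feeding practices". Section 5 sets the testing level: "All tests will be two-sided, at 5% level of significance".

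The analysis steps are in the subsection numbered 5.4. General comment (a) concedes that the study is badly short of power for equivalence analysis, above all for dichotomous outcomes, and chooses conventional difference testing first. Step b is a global test across the four dose groups, by ANCOVA or logistic regression with covariates. Step c then reads: "For all analyses, if the global null hypothesis is rejected at 0.05 level, then we will perform post-hoc pairwise comparisons of all four groups". Steps f to h add adjusted 90% intervals against equivalence margins, but only for the four quasi-continuous outcomes. Step i provides that, where results are inconclusive, all LNS groups are pooled and compared with control.

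Section 7 carries the same condition into the table list. Each of Tables 4b, 5b and 6b has the note "This table, with pairwise comparisons, will be prepared if overall tests are significant". The shells that are always prepared have columns for N, missing, Control, the three doses, All and one P-value. The footnote to Table 4a says: "Values presented are unadjusted prevalences. Statistical tests are for adjusted analyses".

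Main SAP 12.4 gives the general rule: "Regardless of results in hypothesis testing, the calculated ratios and differences in between-group comparisons will be complemented with confidence intervals". It covers binary outcomes as well as quantitative ones.

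**The concern.** Under a hypothesis of no impact, the supportive finding is a non-significant global test. For the yes/no outcomes that is exactly the case in which the plan tabulates no contrast. A P-value above 0.05 without an interval cannot separate a supplement that leaves feeding unchanged from data too imprecise to tell. The percentages that are printed do not repair this, because they are unadjusted while the P-value comes from an adjusted model. The effect actually tested, and its precision, are not tabulated.

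The appendix says it was motivated by worry that LNS may displace breastfeeding or local foods. The interval matters because it shows how large a displacement the data still allow.

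**Working it through.** **What is tabulated when the global P exceeds 0.05**

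| Yes/no outcome | Ungated interval on a related score (steps f-h) | LNS-control estimate and CI for the outcome itself |
|---|---|---|
| No breastfeeding | none | none |
| Six or more feeds | none | none |
| Four or more food groups | none | none |
| No animal-source food | count of animal-source groups | none |
| No fruit or vegetables | count of fruit/vegetable groups | none |
| Lowest animal-source tertile | 7-day animal-source score | none |
| Lowest fruit/vegetable tertile | 7-day fruit/vegetable score | none |

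The last four rows are cut from, or built on essentially the same items as, scores that do receive an interval. The first three have no such companion. Figure 2, an example figure, would put intervals on the group breastfeeding prevalences, not on differences between groups.

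**How often the condition would hide a real fall**

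The appendix states no power or margin for these outcomes, so there is no figure to reproduce. The following is an illustration.

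Inputs:
- 1932 infants in six groups (SAP section 2).
- Assumed equal split: 1932/6 = 322 per arm. With milk and milk-free arms merged, this gives 322, 322, 644 and 644 at 0, 10, 20 and 40 g.
- Assumed 90% with data: about 290, 290, 580 and 580.
- Assumed true effect: every LNS group 5 points below control. No covariate adjustment.

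Global test on 3 df, critical value 7.81. With n = 290 controls and 5n LNS children, the noncentrality is λ = d² × (5n/6) / [p̄(1 − p̄)], where p̄ = p − 5d/6.

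Numerator: 0.05² × (5 × 290/6) = 0.0025 × 241.67 = 0.604.

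| Control prevalence | p̄ | λ | Power | Missed |
|---|---|---|---|---|
| 85% | 0.808 | 3.90 | 35% | 65% |
| 70% | 0.658 | 2.69 | 25% | 75% |
| 50% | 0.458 | 2.43 | 23% | 77% |

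At more extreme prevalences power is higher: about 44% from 90% and 61% from 95%.

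The pooled two-group test of step i, on the same inputs, has power of about 51%, 37% and 34% from 85%, 70% and 50%.

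**What an interval would have shown**

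95% half-width = 1.96 × √[p(1 − p)(1/n₁ + 1/n₂)].
- 20 g or 40 g v control at 85%: 1.96 × √[0.1275 × (1/290 + 1/580)] = 5.0 points.
- 10 g v control at 50%: 1.96 × √[0.25 × (2/290)] = 8.1 points.

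So a non-significant result could easily sit alongside an interval that includes a 5-point fall. The reader would need to see that.

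**The case against.** The strongest reply is step i. It applies to each outcome and does not depend on a significant global test, so a reader might infer too much from the 65% to 77%. Those figures are the chance that the global test misses a 5-point fall and the dose-specific tables are not made. They are not the chance that no contrast of any kind is shown. This stands. What remains is that step i does not define inconclusive for yes/no outcomes, aims at power to detect differences, and names no estimate, interval or table.

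A reader might also infer a direct breach of main SAP 12.4. The text does not go that far. Section 12.4 attaches intervals to contrasts that are calculated, and Appendix 05 does not expressly adopt it, whereas Appendices 01, 02 and 04 do. But Appendix 05 describes itself as nested in the main plan and has no confidence-interval section replacing 12.4. Leaving a contrast uncalculated because a test was non-significant defeats the purpose of that rule.

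Three further points have weight. The appendix nowhere says that P>0.05 will be reported as no impact, and it promises to explain the lack of power in the discussion of any publication. Crude differences can be read off the printed percentages. The shells are for a manuscript group to examine, on a secondary outcome, and gated post-hoc comparison is a common choice. None of these supplies the adjusted estimate or its interval.

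It is also tempting to object to the footnote on the diet-quality tables, "Decision on presenting means or medians will be made after examination of distributions". That concerns only the descriptive summary. Steps f and g still give mean-difference intervals for those scores, so it adds nothing to this point.

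**Conclusion.** The point holds in a limited form. For the yes/no feeding outcomes, dose-specific LNS-control estimates and intervals are not planned after a non-significant global test, and the pooled fallback is too loosely specified to fill the gap. It matters most for no breastfeeding, six or more feeds and four or more food groups. It is a departure from the general rule in 12.4, not a literal breach.

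The size is illustrative. With 322 per arm, 90% retained, a uniform 5-point fall and no covariates, the global test misses the fall in about 65% to 77% of trials at control prevalences of 85% to 50%, and less often at prevalences of 90% or above. The conclusion itself rests on the text and does not depend on these assumptions. This is a change that should be made; it does not touch the trial's primary analysis.

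**What to change.** Remove the condition from Tables 4b, 5b and 6b. For each yes/no outcome and visit, always report the adjusted LNS-control difference or ratio with its confidence interval, for each dose and for all LNS groups combined, whatever the global P-value. Say whether the multiplicity adjustment of step h applies to these intervals.

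Keep the global test and step c only for deciding which contrasts may be called significant. With the pooled contrast always reported, step i no longer needs an undefined trigger for these outcomes. Add a sentence that P>0.05 alone will not be reported as no impact, and one that main SAP 12.4 applies to Appendix 05.

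The cost is SAP wording and one more set of table columns. The estimates come from models the plan already fits, and no new data are needed.

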	3.1 Data Cleaning
	3.2 Outliers
	3.3 Software
	3.4 Analysis
	3.4.1 Summary Baseline Characteristics
	3.4.2 Summary of Short- and Long-term WTP
	3.4.3 Factors Associated with WTP
4.	References9
5.	Tables10
	Table 1: Baseline Respondent, Household, and Maternal Characteristics
	Table 2: Average WTP for a Week's Supply of LNS and LP at Baseline
	Table 3: Average WTP for a Week's Supply of LNS and Likuni Phala at Baseline by Treatment Group and Perspondent
	Table 4: A verses Long Term WTP for LNS and Likupia Phale at Pasalina
	Table 4. A verage Long-Term wirr for Livs and Likuma ritata at Baseline
	Table 5: Average Long-Term WTP for LNS and Likuni Phala at Baseline by Treatment Group
	and Kespondent
	Table 6: Regression Results - Baseline WTP for a Week's Supply 16
	Table 7: Regression Results - Long-Term Baseline WTP 18

1. Brief Introduction and Motivation

In this paper we will present baseline estimates of hypothetical willingness-to-pay (WTP) for a small-quantity preventative lipid-based nutrient supplement (LNS) product formulated for consumption during early childhood, from approximately 6-24 months. Using contingent valuation methods, we elicited hypothetical WTP for a week's supply of LNS from households participating in the iLiNS-DOSE randomized control nutrition trial in Malawi. As a comparator, we also elicited hypothetical WTP for a week's supply of Likuni Phala (LP), a familiar, locally-available product commonly in this iLiNS study area. For both LNS and LP, after eliciting WTP for a week's supply of the product, we used a set of follow-up questions to assess hypothetical WTP in the long-term (i.e., WTP for a week's supply regularly over the coming year).

Preventative LNS products are intended to be consumed daily for many months as a supplement to breast milk and traditional foods (Dewey and [name] 2012; Nutriset 2011). This is in contrast to ready-to-use therapeutic foods such as Plumpy'Nut©, which are primarily used in emergency settings and are administered in relatively large doses over a short period of time to treat children with severe acute malnutrition. While the international donor community has historically purchased and distributed therapeutic nutritional products for severely malnourished children for free via public channels, the differences in usage of preventative LNS products coupled with the potentially large and heterogeneous population of women and children who may benefit from them will make full subsidization of preventative LNS products much more expensive and less likely (Lybbert 2012). Thus, a hybrid distribution system that reaches target consumers through both public channels and retail markets may be recommended.

In this hybrid setting, in addition to the opportunity costs associated with procuring and consuming preventative LNS products, some households may also be required to pay for them. Our estimates of willingness-to-pay (WTP) for LNS will shed light on household valuation of LNS and the factors that influence WTP.¹ Moreover, our data on WTP for LP will provide a benchmark from which we can evaluate WTP for LNS relative to a familiar, locally-available product. This collection of results will provide a starting point for characterizing demand for LNS, which in turn may guide policy decisions regarding the price LNS consumers might be expected to pay as well as help establish a targeting mechanism to distribute LNS.

2. Description of Variables

The following sections describe the dependent and explanatory variables that will be used to model WTP. Note that the baseline contingent valuation survey was to be administered within a

¹ The randomized trial is evaluating the efficacy of LNS for childhood consumption.

few weeks of enrollment.² Figure 1 depicts the relationship between infant enrollment into the randomized trial and the actual timing of each round of the contingent valuation survey.³ Time is measured in weeks from the birth of the child. The grey boxes indicate the approximate range of time when enrollment and contingent valuation surveys were administered.

FIGURE 1: TIMELINE OF ILINS-DOSE INTERVENTION AND CONTINGENT VALUATION (CV) SURVEY

